6.0 Study Visit Procedures (See Appendix A)

6.1 Screening/Randomization Visit

The investigator or designee will:

- Obtain written informed consent
- Obtain relevant medical history
- Determine eligibility
- Conduct pregnancy test (WOCBP only)
- Obtain blood samples for research laboratory tests
 - Research labs include: D-dimer, thrombin-antithrombin, and calibrated automated thrombography, IL-6, sVCAM
- Assess concomitant medication use

Impact of Daily Prophylaxis Dose Anticoagulation with a Factor Xa Inhibitor (Apixaban) in Patients with Sickle Cell Disease

- Randomize subject
- Perform Pain Score
- Distribute Pain log
- Perform Patient Reported Outcome Computerized Questionnaire (PROMIS)
- Install SMART app on subject's phone or provide subject with a device

6.1.2 Observational Period (30 days)

Via a telephone contact at 2 weeks, the investigator or designee will:

- Assess concomitant medication use
- Review pain log completion guidelines
- Assess adverse events

6.1.3 Month 1

The investigator or designee will:

- Obtain blood samples for research laboratory tests
 - Research labs include: D-dimer, thrombin-antithrombin, and calibrated automated thrombography.
- Assess concomitant medication use
- Perform Pain Score
- Dispense study drug
- Assess pain log completion compliance
- Assess adverse events

6.1.4 Month 1, 2, 3, 4, 5, 6, 7 and 8 (telephone) – 2 weeks following last clinic visit

Via a telephone contact, the investigator or designee will:

- Assess concomitant medication use
- Review pain log completion guidelines
- Assess adverse events

6.1.5 Month 2

The investigator or designee will:

- Assess concomitant medication use
- Perform Pain Score
- Dispense study drug
- Assess pain log completion compliance
- Assess adverse events
- Perform Patient Reported Outcome Computerized Questionnaire (PROMIS)

6.1.6 Month 3

The investigator or designee will:

- Obtain blood samples for research laboratory tests
 - Research labs include: D-dimer, thrombin-antithrombin, and calibrated automated thrombography.
- Assess concomitant medication use
- Perform Pain Score
- Assess study drug compliance

Impact of Daily Prophylaxis Dose Anticoagulation with a Factor Xa Inhibitor (Apixaban) in Patients with Sickle Cell Disease

- Dispense study drug
- Assess pain log completion compliance
- Assess adverse events

6.1.7 Month 4

The investigator or designee will:

- Assess concomitant medication use
- Perform Pain Score
- Assess study drug compliance
- Dispense study drug
- Assess pain log completion compliance
- Assess adverse events

6.1.8 Month 5

The investigator or designee will:

- Obtain blood samples for research laboratory tests
 - Research labs include: D-dimer, thrombin-antithrombin, and calibrated automated thrombography, IL-6, and sVCAM.
- Assess concomitant medication use
- Perform Pain Score
- Assess study drug compliance
- Dispense study drug
- Assess pain log completion compliance
- Assess adverse events

6.1.9 Month 6

The investigator or designee will:

- Assess concomitant medication use
- Perform Pain Score
- Assess study drug compliance
- Dispense study drug
- Assess pain log completion compliance
- Assess adverse events

6.1.10 Month 7 (End of Treatment)

The investigator or designee will:

- Assess concomitant medication use
- Perform Pain Score
- Assess study drug compliance
- Assess pain log completion compliance
- Assess adverse events
- Perform Patient Reported Outcome Computerized Questionnaire (PROMIS)

6.1.11 Month 8 (Follow-Up)

The investigator or designee will:

- Obtain blood samples for research laboratory tests

Impact of Daily Prophylaxis Dose Anticoagulation with a Factor Xa Inhibitor (Apixaban) in Patients with Sickle Cell Disease

- Research labs include: D-dimer, thrombin-antithrombin, and calibrated automated thrombography.
- Assess concomitant medication use
- Perform Pain Score
- Assess pain log completion compliance
- Assess adverse events

7.0 Study Duration

Enrollment for this study will be completed within the first 12 months (average 5 patients per month), followed by 8 months to allow completion of study by all patients.

8.0 Data and Safety Monitoring Board.

The Duke University Data and Safety Monitoring Board (DSMB) is a Committee that has been established for the purpose of monitoring clinical studies. The DSMB has multiple responsibilities including:

- Assessing risk and complexity of those clinical trials that have been submitted for review
- Determining the appropriate level of data and safety monitoring
- Reviewing the reports of all serious adverse events (SAEs) that have been experienced by participants in those active clinical trials that are being monitored by the DSMB
- Reviewing the regularly submitted (usually at least yearly) data and safety monitoring reports that are required of all active clinical trials.
- Recommending appropriate actions (closure, increased monitoring, etc.) to the Principal Investigator.

9.0 Data Safety and Monitoring Plan

We will be using the descriptive terminology developed by the National Cancer Institute for use in reporting adverse events: Common Toxicology Criteria for Adverse Events (CTCAE) version 4.0, dated May 29, 2009. The website for the CTCAE is <http://evs.nci.nih.gov/ftp1/CTCAE/About.html>. The CTCAE includes a grading (severity) scale for each adverse event term.

9.1 Adverse Event Reporting

9.1.1 Collection of Safety Information

An *Adverse Event (AE)* is defined as any new untoward medical occurrence or worsening of a pre-existing medical condition in a patient or clinical investigation subject administered an investigational (medicinal)

product and that does not necessarily have a causal relationship with this treatment. An AE can therefore be any unfavorable and unintended sign (including an abnormal laboratory finding, for example), symptom, or disease temporally associated with the use of investigational product, whether or not considered related to the investigational product.

Adverse events can be spontaneously reported or elicited during open-ended questioning, examination, or evaluation of a subject. (In order to prevent reporting bias, subjects should not be questioned regarding the specific occurrence of one or more AEs.)

Impact of Daily Prophylaxis Dose Anticoagulation with a Factor Xa Inhibitor (Apixaban) in Patients with Sickle Cell Disease

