1.0 Introduction and Background

In patients with SCD, the use of low dose anticoagulation as an outpatient may lead to a significant decrease in morbidity and as a result, decrease healthcare utilization and costs. Sickle cell disease (SCD) is most commonly affected by recurrent painful vaso-occlusive crisis (VOC) and although greater than 50% of patients with SCD have significant daily pain, only 5% of patients actually seek medical attention (Smith, 2008). Importantly, hospitalizations account for up to 90% of the medical care costs for patients with SCD (Yang, 1995). Review of data from the National Center for Health Statistics revealed the average direct costs per hospitalization (in 1996 dollars) was estimated at \$6300, for a total direct cost of \$475 million per year. The use of anticoagulation in SCD builds upon recent studies including our own (Shah, 2012; Ataga, 2007; Francis, 1989; Stuart 2001) which document a hypercoagulable state and has been found to be promising in smaller past studies.

Although few studies have attempted to evaluate clinical pain scores in the context of anticoagulation, several studies have examined the effects of anticoagulation on the coagulation system in SCD. Wolters et al documented that use of acenocoumarol at a mean INR of 1.64 resulted in a 50% decrease in plasma prothrombin fragment 1+2 in SCD patients during steady state. However, clinical evaluation was not performed in this initial small study (Wolters, 1995). Subsequently, Ahmed et al measured D-dimer in 37 sickle cell patients treated with low dose warfarin (mean dose of 1 mg) while in crisis. Their results revealed a significant decrease in D-dimer levels in patients treated with warfarin (Ahmed, 2004). These studies also documented no bleeding with low dose anticoagulation, along with the decrease in hypercoagulable markers.

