Following randomization by IDS, and initial blood draw (Figure 1), patients will be given a daily pain log. Patients will record daily pain scores and return in 1 month (+/- 5 days) at which time patients will then be given a 1 month supply of study drug. Patients will return monthly (+/- 5 days) to return daily pain logs, verify compliance to medication, review completion of daily pain logs, and give additional study drug for the next month. Patients must adhere to daily administration of study drug and miss no more than 2 doses per week. Clinical pain scores will also be performed with each visit. The primary pain assessment tool will be a 10-cm horizontal visual analog scale (VAS), with “0” corresponding to no pain at one end and “10” indicating the worst pain at the other. The daily pain log will include the VAS and if the patient classifies their pain as ‘crisis’ or not. Patients will be called monthly between in person visits to assess for AE/SAE and to reinforce the importance of medication compliance. Along with the VAS, there will be novel methods of pain assessment that may prove to better measure the impact of pain in these patients. One method is the use of the validated PROMIS format. PROMIS uses a 5-point Likert-type format with response options ranging from never to always. A total score is calculated by obtaining a sum of scores across items, with higher scores indicating greater impact of the particular domain to a patient’s daily living. Patients will have PRO performed on enrollment, after 1 month’s use of study drug and at the end of 6 months’ use of study drug. Patients will complete PROMIS on a mobile device and have all results

Impact of Daily Prophylaxis Dose Anticoagulation with a Factor Xa Inhibitor (Apixaban) in Patients with Sickle Cell Disease

recorded on the Duke secure server for further information. The second, a SMART application will be installed on patient's iPhones/iPads at their request to assist with monitoring of symptoms. Patients without an Apple device can have one loaned to them until completion of the study.

The devices will be returned to the study PI or coordinator per agreement at the time of enrollment. Patients admitted to the hospital will continue their study drug or placebo unless deemed medically inappropriate by admitting physician. Patients upon discharge are to resume study drug per supervision of study

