9.3 Collection and Reporting

Adverse events can be spontaneously reported or elicited during open-ended questioning, examination, or evaluation of a subject. (In order to prevent reporting bias, subjects should not be questioned regarding the specific occurrence of one or more AEs.)

If known, the diagnosis of the underlying illness or disorder should be recorded, rather than its individual symptoms. The following information should be captured for all AEs: onset, duration, intensity, seriousness, relationship to investigational product, action taken, and treatment required. If treatment for the AE was administered, it should be recorded in the medical record.

The investigator shall supply the sponsor and Ethics Committee with any additional requested information, notably for reported deaths of subjects.

All AE/SAEs will be reported to the DSMB and BMS. The DSMB will review these data at their regular meeting and notify the Principal Investigator if safety appears to be an issue. After 12 months of this study (or completion of 20 patients, whichever comes first), all of the safety data, including information on any deaths, will be presented to the DSMB in a tabular format. The investigators will also prepare an overall report to accompany the tables. The DSMB will review the report and determine if there is a safety concern. If there are significant adverse events, the DSMB may recommend that the study be terminated. All AE/SAEs will be included in the final study report.

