9.3.1 Serious Adverse Events

Following the subject’s written consent to participate in the study, all SAEs must be collected, including those thought to be associated with protocol-specified procedures. All SAEs must be collected that occur within 70 days of discontinuation of dosing of the investigational product. If applicable, SAEs must be collected that relate to any later protocol-specified procedure (e.g., a follow-up skin biopsy). The investigator should notify BMS of any SAE occurring after this time period that is believed to be related to the investigational product or protocol-specified procedure.

All SAEs whether related or unrelated to the study drug, apixaban, must be immediately reported to BMS (by the investigator or designee) within 24 hours of becoming aware of the event. If only limited information is initially available, follow-up reports are required. The original SAE form must be kept on file at the study site.

All SAEs should be faxed or emailed to BMS at:

Global Pharmacovigilance & Epidemiology
Bristol-Myers Squibb Company
[contact]
Email: [contact]

Impact of Daily Prophylaxis Dose Anticoagulation with a Factor Xa Inhibitor (Apixaban) in Patients with Sickle Cell Disease

Serious adverse events, whether related or unrelated to investigational product, must be recorded on the SAE page and reported expeditiously to BMS (or designee) to comply with regulatory requirements. An SAE report should be completed for any event where doubt exists regarding its status of seriousness.

All SAEs must be immediately reported by confirmed facsimile transmission (fax) and mailing of the completed SAE page. In some instances where a facsimile machine is not available, overnight express mail may be used. If only limited information is initially available, follow-up reports are required. (Note: Follow-up SAE reports should include the same investigator term(s) initially reported.) In selected circumstances, the protocol may specify conditions that require additional telephone reporting.

If the investigator believes that an SAE is not related to the investigational product, but is potentially related to the conditions of the study (such as withdrawal of previous therapy, or a complication of a study procedure), the relationship should be specified in the narrative section of the SAE page.

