9.3.7 Adverse Events of Special Interest

Wherever possible, timely confirmation of initial liver-related laboratory abnormalities should occur prior to the reporting of a potential adverse event (AE) of special interest. All occurrences of potential adverse event of special interest, meeting the defined criteria, must be reported as SAEs (see Section 7.2.1 for reporting details).

In this study, the following adverse events are to be reported to BMS, regardless of whether these reports are classified as serious or unexpected:

- Potential or suspected cases of liver injury including but not limited to liver test abnormalities, jaundice, hepatitis or cholestasis..

Impact of Daily Prophylaxis Dose Anticoagulation with a Factor Xa Inhibitor (Apixaban) in Patients with Sickle Cell Disease

SAE Reconciliation

The investigator will reconcile the clinical database SAE cases transmitted to BMS Global Pharmacovigilance (GPV&E). Reconciliation will occur every three months and once just prior to database lock/Final Study Report (FSR). The investigator will request a safety data reconciliation report to [contact]. BMS GPV&E will e-mail upon request from the investigator, the GPV&E reconciliation report. The data elements listed on the GPV&E safety data reconciliation report will be used for case identification purposes. If the investigator determines a case was not transmitted to BMS GPV&E, the case will be sent immediately.

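### Staff may not ask about specific adverse events and the supplied text has no bleeding item, so non-serious bleeding is at risk of under-ascertainment in this anticoagulant trial

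*Combined protocol and SAP*

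**What the plan says.** Section 9.1.1 describes how adverse events are found: "Adverse events can be spontaneously reported or elicited during open-ended questioning, examination, or evaluation of a subject". A restriction follows at once, that "subjects should not be questioned regarding the specific occurrence of one or more AEs". Section 9.3 repeats both sentences and gives the reason: "In order to prevent reporting bias, subjects should not be questioned regarding the specific occurrence of one or more AEs".

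Adverse events are assessed often. Section 4.1 says "Patients will be called monthly between in person visits to assess for AE/SAE". Section 6 lists an adverse event assessment at the two-week call in the observation period, at each visit from Month 1 to Month 8, and at the calls two weeks after clinic visits. Events are graded by CTCAE version 4.0 (Section 9.0).

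For serious events, Section 9.3.1 requires that after consent "all SAEs must be collected, including those thought to be associated with protocol-specified procedures", and collection continues to 70 days after dosing stops. The note in Section 9.1.2 removes from the SAE definition an emergency visit of under 24 hours without admission, unless the event is judged an important medical event or life-threatening.

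Section 9.3.7 names one event of special interest: "Potential or suspected cases of liver injury including but not limited to liver test abnormalities, jaundice, hepatitis or cholestasis". Bleeding is mentioned only in the background (Section 1.0), which says of earlier studies: "These studies also documented no bleeding with low dose anticoagulation". The same section also reports no bleeding in the long-term heparin series.

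**The concern.** Bleeding is the expected harm of an anticoagulant, and the plan's own background reports its absence as a result of earlier low-dose studies. Yet the plan gives staff no prompt to ask about it and states a rule against doing so. A nosebleed, gum bleeding, heavier menstrual loss or a bleed treated and released may not come up in answer to a general question, particularly in patients whose attention is on daily pain.

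The trial is described as a feasibility study. Its bleeding count will inform any decision about a larger trial, and the DSMB will look at tabulated safety data after 12 months or 20 completed patients, whichever comes first. A low or zero count is reassuring only if the method of collection would have found the events.

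The stated reason for the rule, preventing reporting bias, carries less weight here. In a double-blind placebo-controlled trial, one fixed question put identically to both arms makes ascertainment uniform and gives neither arm an advantage.

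**Working it through.** The plan states no bleeding rate, capture fraction or bleeding power, so there is no figure to reproduce. The check has two parts: a comparison of the text, and a calculation for scale.

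**Which routes could pick up a bleed?**

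- *Serious bleed.* Collected as an SAE under Sections 9.1.2 and 9.3.1. The questioning rule does not alter that duty.
- *Bleed treated in an emergency visit under 24 hours, no admission, not judged important or life-threatening.* Not an SAE under the Section 9.1.2 note. It depends on the general adverse event enquiry.
- *Minor bleed at home.* Also depends on the general enquiry.
- *Examination or evaluation.* Allowed by Section 9.1.1, but the visit lists in Section 6 schedule no physical examination and no blood count. The research bloods named are D-dimer, TAT and CAT, with IL-6 and sVCAM at some visits. Section 4.1 implies that creatinine, platelets and transaminases are looked at during the study, but it does not mention haemoglobin.
- *CTCAE grading.* Grades an event once reported; it does not elicit one.

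In the supplied text, then, non-serious bleeding rests largely on open questions, with a direct question barred.

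**Scale**

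Inputs: 30 patients per arm (Section 3.0). The true proportion of patients with a bleed, p, and the fraction captured, c, are assumptions. The recorded proportion is p × c.

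1. Upper limit with zero recorded bleeds. One-sided 95% limit for the recorded rate: 1 − 0.05^(1/30) = 0.095. Limit for the true rate: 0.095 / c.
   - c = 1.0: 9.5%
   - c = 0.8: 0.095 / 0.8 = 11.9%
   - c = 0.5: 0.095 / 0.5 = 19.0%

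   This applies c to every bleed. Serious bleeds have their own route, so 19% is the outer end for that choice of c.

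2. Chance of recording no bleed in an arm: (1 − p × c)^30.
   - p = 5%: 21% at c = 1.0; 29% at c = 0.8; 47% at c = 0.5
   - p = 10%: 4% at c = 1.0; 8% at c = 0.8; 21% at c = 0.5
   - p = 20%: 0.1% at c = 1.0; 0.5% at c = 0.8; 4% at c = 0.5

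3. Effect on the comparison, for an assumed 30% versus 10% and the same c in both arms. The ratio stays at 3. The difference shrinks from 0.30 − 0.10 = 0.20 to 0.15 − 0.05 = 0.10 at c = 0.5. One-sided 0.05 power (normal approximation, 30 per arm) falls from 0.62 at c = 1.0 to 0.52 at c = 0.8 and 0.36 at c = 0.5.

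**The case against.** The best defence is that the plan does not rely on patients volunteering events. It allows open-ended questioning, examination and evaluation, and someone enquires about every two weeks. This stands. A reader might infer from the rule that a non-serious bleed is recorded only if the patient brings it up, or that bleeding is bound to be under-counted. The documents support neither reading: the sentence before the rule contradicts the first, and no capture rate is given that could establish the second.

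A reader might also infer that leaving bleeding off the Section 9.3.7 list means bleeds go unreported. It does not. That list governs reporting to the manufacturer, and Section 9.3 already sends all adverse events to the DSMB and the manufacturer and includes them in the final report.

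Nor is the elicitation method the only limit on what the trial can say about bleeding. At 30 per arm, power for 30% versus 10% is only 0.62 with full capture, and neither specific aim is to estimate bleeding. The 9.5% limit itself comes from the sample size alone. This stands too, but it argues against losing events from a count that is already small.

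Open-ended elicitation is a deliberate choice with a stated reason, so this is a design criticism and not an internal contradiction. The contents of Appendix A and Figure 1 are not in the supplied text, so a bleeding item there cannot be excluded.

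The defence does not answer one point. Frequent contact cannot substitute for a direct question when the rule bars that question at every contact.

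**Conclusion.** The point holds as a risk of under-ascertainment of minor and other non-serious bleeds. It does not extend to serious bleeds, and it is not a demonstrated under-count.

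The expected consequence is lower absolute bleeding rates and a smaller visible difference between arms. Bias towards one arm is not expected, provided blinding holds and capture is similar in both arms.

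The size depends wholly on an assumed capture fraction. With zero recorded bleeds among 30 patients, the upper limit for the true rate is 9.5% at full capture and about 19% at half. At a true rate of 10%, halving capture raises the chance of an arm showing no bleeds from 4% to 21%. These figures show why capture matters at this sample size; they do not estimate what will happen.

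The plan should be changed because the remedy is small and the bleeding count is central to judging a further trial. Confidence is medium, given the material not shown.

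**What to change.** - In Sections 9.1.1 and 9.3, exempt bleeding from the rule that only open questions may be asked. Keep the rule for other events.
- In Section 6, add one fixed bleeding question (yes/no and site, with a CTCAE grade assigned by staff), asked in the same words in both arms at each existing visit and call. The answer form then also defines what counts as a bleed.
- State that bleeding will be tabulated by arm in the DSMB report and in the final report.
- Do not add bleeding to Section 9.3.7. Events of special interest meeting that section's criteria must be reported as SAEs, so an unqualified entry could turn minor bleeds into 24-hour reports under Section 9.3.1.

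The cost is one question at contacts that already take place, plus one table. The downside is that more minor events will be recorded in both arms. The change concerns data collection only.
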